### **6.5.2. Hematologic Improvement**

[figure not shown]
Hematologic improvement will be assessed by the investigators and retrospectively by a blinded IRAC according to IWG MDS HI criteria ([Appendix H](#)) through collection of transfusion records and central hematology parameters.

### **6.5.3. Survival**

Refer to Section 6.3 for survival follow-up.

[figure not shown]
## 6.9. Quality-of-Life

Two instruments, the European Organization for Research and Treatment of Cancer Quality-of-Life questionnaire (EORTC QLQ-C30) and EuroQoL Group EQ-5D, will be used for HRQoL.

The EORTC QLQ-30 ([Aronson, 1993](#)) is a validated quality of life measure applicable to subjects with any cancer diagnosis. It is composed of 30 items that address general physical symptoms, physical functioning, fatigue and malaise, and social and emotional functioning. Subscale scores are transformed to a 0 to 100 scale, with higher scores on functional scales indicating better function and higher scores on symptom scales indicating worse symptoms. The EORTC QLQ-C30 is available in many languages. This instrument takes 10 to 15 minutes to administer. The EORTC QLQ-C30 data will be captured using a portable electronic tablet computer. See [Appendix I](#) for an example.

The EQ-5D is a standardized instrument for use as a measure of health outcome. It provides a simple descriptive profile and a single index value for health status, and is applicable to a wide range of health conditions and treatments. The EQ-5D is available in many languages and it takes approximately 5 minutes to complete. EQ-5D data will be captured using a portable electronic tablet computer. See [Appendix J](#) for an example.

It is important that every subject completes all assessments of EORTC QLQ-30 and EQ-5D at every specified time point, prior to dosing and prior to interaction with study personnel, to minimize the amount of missing data.

[Redacted]

## 7. DESCRIPTION OF STUDY TREATMENTS

### 7.1. Description of Investigational Product(s)

#### 7.1.1. AG-221

AG-221 will be supplied by Celgene and labeled appropriately as investigational product (IP) for this study.

Celgene Corporation will supply AG-221 50-, 100-, 150- and 200-mg free-base equivalent strength tablets for oral administration. Each tablet is formulated using excipients that are generally regarded as safe and are used in marketed drug products.

All tablets will be packaged in high density polyethylene (HDPE) bottles with a desiccant (silica gel) canister and child resistant closures with heat induction seal. All tablets should be swallowed whole, and should not be broken or chewed.

Bottles of AG-221 tablets must be stored according to the package label. The storage area should be secure and have limited access. AG-221 tablets will be monitored by the Sponsor for stability for the duration of the study.

#### 7.1.2. Azacitidine

Azacitidine will be supplied by Celgene Corporation as a sterile lyophilized powder containing 100 mg of azacitidine and 100 mg of mannitol per vial.

Detailed instructions for preparation of SC azacitidine are provided in [Appendix K](#).

#### 7.1.3. Low-dose Cytarabine

Subjects randomized to LDAC treatment and located in countries where LDAC is designated as non-investigational product (NIP) may have cytarabine sourced locally by the clinical site. Subjects randomized to LDAC treatment and located in countries where LDAC is designated as IP will have cytarabine supplied and packaged by Celgene Corporation.

Please refer to the UK SmPC for more details on available formulations, preparation of SC cytarabine, storage conditions (eg, refrigeration), the approved indications, known precautions, warnings, and adverse reactions of cytarabine.

#### 7.1.4. Intermediate-dose Cytarabine

Subjects randomized to IDAC treatment and located in countries where IDAC is designated as NIP may have cytarabine sourced locally by the clinical site. Subjects randomized to IDAC treatment and located in countries where IDAC is designated as IP will have cytarabine supplied and packaged by Celgene Corporation.

Please refer to the UK SmPC for more details on available formulations, preparation of IV cytarabine, storage conditions (eg, refrigeration), the approved indications, known precautions, warnings, and adverse reactions of cytarabine.

### 7.1.5. Best Supportive Care Only

Refer to Section 8 for details regarding BSC. Please refer to local prescribing information and local therapeutic guidelines for more details on available formulations, preparation, storage conditions (eg, refrigeration), the approved indications, known precautions, warnings, and adverse reactions of BSC (see the current version of prescribing information).

## 7.2. Treatment Administration and Schedule

Study treatment is to be initiated on Day 1 of each treatment cycle. The subject may not receive study treatment for each treatment cycle until all Day 1 procedures have been completed and all doses of study treatment from the prior treatment cycle are accounted for (where applicable). For FCBP subjects, a serum or urine (investigator's discretion under local regulations)  $\beta$ -hCG pregnancy test (sensitivity of at least 25 mIU/mL) must be performed within 72 hours prior to study treatment administration on Day 1 of each treatment cycle and verified negative.

No crossover between any of the treatment options, including the CCR treatment options, will be permitted during the course of study treatment. Any AML therapy other than the study-prescribed treatment is prohibited during the course of study treatment.

Subjects will be monitored for hematologic toxicity and non-hematologic toxicity with the National Cancer Institute (NCI) Common Terminology Criteria for Adverse Events (CTCAE, Version 4.03) used as a guide for the grading of severity. Dosing interruptions or delays, or dose modifications may occur for managing toxicities and/or augmenting treatment response during study treatment.

**Overdose**, as defined for this protocol, refers to AG-221, azacitidine and cytarabine dosing only.

On a per dose basis, an overdose is defined as the following amount over the protocol-specified dose of AG-221, azacitidine and cytarabine assigned to a given subject, regardless of any associated adverse events or sequelae.

PO: any amount over the protocol-specified dose

IV: 10% over the protocol-specified dose

SC: 10% over the protocol-specified dose

On a schedule or frequency basis, an overdose is defined as anything more frequent than the protocol required schedule or frequency.

Complete data about drug administration, including any overdose, regardless of whether the overdose was accidental or intentional, should be reported in the eCRF. See Section 10 for the reporting of AEs associated with overdose.

Subjects can continue to receive study treatment provided that they benefit from study treatment and all protocol-specified criteria for continuing study treatment are met. Study treatment will be discontinued if the investigator has alternative therapies (eg, HSCT) and/or considers study treatment to be no longer beneficial to the subject, or the rapidity of change of disease state renders it unacceptable for further study treatment in the judgment of the investigator.

Refer to Section 11.1 for events that are considered sufficient reasons for discontinuing a subject from study treatment.

### **7.2.1. AG-221 Treatment**

Subjects randomized to the AG-221 treatment arm will receive continuous 28-day cycles of AG-221 100 mg PO QD for 28 days. In addition, subjects may receive BSC per standard institutional practice and as deemed necessary by the investigator. In order to optimally benefit from the AG-221 treatment, the investigator should aim to treat subjects for at least 6 cycles or as long as subjects continue to benefit from the treatment until the End of Trial. Subjects may be discontinued from the treatment for any of the reasons detailed in Section 11.1.

#### **7.2.1.1. Dispensation and Administration of AG-221**

AG-221 will be dispensed on Day 1 of each treatment cycle and a quantity of AG-221 only sufficient for one treatment cycle will be dispensed. Subjects should be instructed to open the AG-221 packaging as close as possible to when they are going to take AG-221, inspect each AG-221 tablet and only take tablets that are totally intact (subjects should be instructed to return any tablet not totally intact to the clinic).

Subjects should be instructed to take their daily dose at approximately the same time each day. Each dose should be taken with a glass of water and consumed over as short a time as possible. Subjects should be instructed to swallow tablets whole and to not chew the tablets.

All efforts should be made to administer AG-221 on all of the scheduled days of each 28-day treatment cycle. A dose missed earlier in a day can be made up later that day as long as it is taken within 6 hours after the missed dose. If more than 6 hours have elapsed, then that dose should be omitted, and the subject should resume treatment with the next scheduled dose. Any missed doses should not be taken beyond the last scheduled day of AG-221 administration, but should be returned by the subject for AG-221 accountability.

If vomiting occurs shortly after a dose of AG-221 is administered, that dose should not be made up later the same day. The subject should continue with the dosing schedule on the next day and inform the investigator about the vomiting event at the next visit.

#### **7.2.1.2. Dose Modifications for AG-221**

The investigator should contact the Medical Monitor for guidance on AG-221 dose modification, if needed.

##### **Dose modification due to toxicities**

If a certain level of toxicity (eg, Section 7.2.1.3) is observed after initiation of AG-221 treatment and considered as possibly or probably related to AG-221 treatment, AG-221 dosing can be interrupted or delayed. Upon resolution of the toxicity, dosing may be resumed with a one-level dose reduction from 100 mg QD to 50 mg QD. Any subject who is unable to tolerate 50 mg QD of AG-221 should be discontinued from study treatment.

If treatment is modified during the course of the study and benefit is demonstrated with a reduced level of dose, then that dose level should be maintained during the subsequent treatment cycles that are given unless toxicity develops. However, once reduced, if there is a need for augmenting treatment response as defined below, the AG-221 dose may be subsequently re-escalated back to the starting dose (ie, 100 mg QD), provided that the starting dose is tolerable.

### **Dose escalation for augmenting treatment responses**

The AG-221 dose for the subsequent treatment cycles that are given may be increased from 100 mg QD to 200 mg QD if the following occurs:

- ANC  $< 0.5 \times 10^9/L$  after being on AG-221 for the first cycle without  $\geq$  Grade 3 AEs suspected by the investigator to be related to AG-221; or
- no partial remission (PR) achieved after being on AG-221 for at least 2 cycles without  $\geq$  Grade 3 AEs suspected by the investigator to be related to AG-221; or
- evidence of morphologic relapse or PD

If benefit is demonstrated with an increased level of dose, then that dose level should be maintained during the subsequent treatment cycles that are given. However, once increased, the AG-221 dose may be reduced if a certain level of toxicity (eg, Section 7.2.1.3) is observed and considered as possibly or probably related to AG-221 treatment. A maximum of 3 steps of AG-221 dose reduction, stepwise first from 200 mg QD to 150 mg QD, second from 150 mg QD to 100 mg QD, and then last from 100 mg QD to 50 mg QD, are permitted in the event of toxicities, depending on the dose that the subject is on. Once reduced, the AG-221 dose should not be re-escalated unless there is evidence of morphologic relapse or PD. Any subject who is unable to tolerate 50 mg QD of AG-221 should be discontinued from study treatment.

### **7.2.1.3. Reference Toxicities During AG-221 Treatment**

#### **Hematologic toxicities**

Hematologic toxicities include clinically significant hematologic toxicities of cytopenia ( $> 50\%$  decrease from baseline [defined in Section 6.2.1]) and/or marrow cellularity  $< 5\%$  on Day 28 or later from the start of AG-221 treatment in a treatment cycle without evidence of leukemia.

#### **Non-hematologic toxicities**

Non-hematologic toxicities include all clinically significant non-hematologic toxicities of  $\geq$  Grade 3 with the exception of  $\geq$  Grade 3 blood bilirubin increases in subjects with a UGT1A1 mutation. In subjects with a UGT1A1 mutation, blood bilirubin increases of  $> 5 \times$  ULN may be considered clinically significant.

#### **QT Prolongation**

Subjects who experience prolongation of the heart rate-corrected QT interval, Fridericia's correction (QTcF) to  $> 480$  msec (Grade  $\geq 2$ ) while treated with AG-221, should be promptly evaluated for causality of the QTc prolongation and managed according to the following guidelines:

- Levels of electrolytes (potassium, calcium and magnesium) should be checked and supplementation given to correct any values outside the normal range.
- Concomitant therapies should be reviewed and adjusted as appropriate for medication with known QT prolonging effects.
- If no other cause is identified and the investigator believes it is appropriate, particularly if QTc remains elevated (after above measures have been implemented, or as determined by the investigator), AG-221 treatment may be interrupted, and an

ECG should be rechecked in approximately 1 week after the QTc prolongation was first observed or more frequently as clinically indicated.

- If QTc has recovered or improved and the investigator believes it is safe to do so, a re-challenge with AG-221 should be considered if held. ECGs should be conducted at least weekly (eg, at every scheduled visit) for 2 weeks following QTc reduction  $\leq 480$  msec.
- If Grade 2 (QTcF  $> 480$  and  $\leq 500$  msec), the dose of AG-221 may be reduced without interruption of dosing. The AG-221 dose may be re-escalated to the prior dose in  $\geq 14$  days after QT prolongation has decreased to  $\leq$  Grade 1.
  - If this is the second occurrence of QT prolongation, administration of AG-221 should continue at a reduced dose (ie, the dose may not be re-escalated).
- If Grade 3 (QTcF  $> 500$  msec), hospitalization for continuous cardiac monitoring and evaluation by a cardiologist should both be considered. Dosing with AG-221 will be interrupted. If QTc returns to within 30 msec of baseline or  $< 450$  msec within 14 days, treatment may be resumed at a reduced dose. The AG-221 dose cannot be re-escalated following dose reduction for Grade 3 QTcF prolongation unless the prolongation was associated with an electrolyte abnormality or concomitant medication.
- If Grade 4 (QTcF  $> 500$  msec or  $> 60$  msec change from baseline with torsade de pointes or polymorphic ventricular tachycardia or signs/symptoms of serious arrhythmia), subjects should be admitted to the hospital for continuous cardiac monitoring and discharged only after review by a cardiologist. Dosing with AG-221 should be permanently discontinued.

### IDH Differentiation Syndrome

Subjects treated with AG-221 (enasidenib) have experienced symptoms of differentiation syndrome, which can be fatal if not treated. Symptoms may include fever, dyspnea, acute respiratory distress, pulmonary infiltrates, pleural or pericardial effusions, rapid weight gain or peripheral edema, lymphadenopathy, bone pain, and hepatic or renal dysfunction. If differentiation syndrome is suspected, initiate corticosteroid therapy and hemodynamic monitoring until symptom resolution.

If differentiation syndrome is suspected, initiate oral or intravenous corticosteroids (eg, dexamethasone 10 mg every 12 hours) and hemodynamic monitoring until improvement. Taper corticosteroids only after resolution of symptoms. Symptoms of differentiation syndrome may recur with premature discontinuation of corticosteroid treatment. If severe pulmonary symptoms requiring intubation or ventilator support, and/or renal dysfunction persist for more than 48 hours after initiation of corticosteroids, interrupt enasidenib until signs and symptoms are no longer severe. Hospitalization for close observation and monitoring of patients with pulmonary and/or renal manifestation is recommended. Enasidenib can be resumed when signs and symptoms improve to Grade 2 or lower.

Further information on diagnosis and treatment of IDH differentiation syndrome can be found in the current version of IDH differentiation syndrome guidance documents.

### Noninfectious Leukocytosis

Subjects with hematologic malignancies treated with enasidenib may experience rapid myeloid cell proliferation, presenting as an increase in WBC count without evidence of infection or signs of IDH differentiation syndrome.

Blood counts should be assessed for noninfectious leukocytosis (defined as WBC greater than  $30 \times 10^9/L$ ) prior to the initiation of enasidenib and monitored at a minimum of every 2 weeks for at least the first 3 months during treatment. Any abnormalities should be managed promptly.

Treatment with hydroxyurea should be initiated, as per standard institutional practices. Interrupt enasidenib if leukocytosis is not improved with hydroxyurea, and then resume enasidenib at 100 mg daily when WBC is less than  $30 \times 10^9/L$ .

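### After an interruption for leukocytosis the protocol resumes AG-221 at 100 mg whatever the earlier dose, which doubles the dose of a subject already reduced to 50 mg for toxicity

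*Protocol*

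**What the plan says.** AG-221 and enasidenib are the same drug, and Section 7.2.1 starts every AG-221 subject at 100 mg once daily. For leukocytosis that hydroxyurea does not control, Section 7.2.1.3 (Noninfectious Leukocytosis) says: "Interrupt enasidenib if leukocytosis is not improved with hydroxyurea, and then resume enasidenib at 100 mg daily when WBC is less than" 30 × 10⁹/L. No exception is stated.

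The other AG-221 dosing rules tie the dose to the subject's history:

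- **Section 7.2.1.2, dose modification due to toxicities.** Once a related toxicity resolves, "dosing may be resumed with a one-level dose reduction from 100 mg QD to 50 mg QD". If "benefit is demonstrated with a reduced level of dose, then that dose level should be maintained", unless further toxicity develops. Where response needs augmenting, the dose may be "re-escalated back to the starting dose (ie, 100 mg QD), provided that the starting dose is tolerable".
- **Section 7.2.1.2, dose escalation.** For a subject who had been escalated: "Once reduced, the AG-221 dose should not be re-escalated unless there is evidence of morphologic relapse or PD".
- **Section 7.2.1.3, QT Prolongation.** After Grade 3, if QTc recovers in time, "treatment may be resumed at a reduced dose". Then: "The AG-221 dose cannot be re-escalated following dose reduction for Grade 3 QTcF prolongation", except where an electrolyte problem or another drug was involved. On a second occurrence, "administration of AG-221 should continue at a reduced dose (ie, the dose may not be re-escalated").

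The differentiation syndrome and tumor lysis rules in Section 7.2.1.3 name no resumption dose. The leukocytosis rule is the only one in that section that fixes a resumption dose in milligrams. The SAP does not address the point.

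**The concern.** A fixed resumption dose is harmless for a subject who was on that dose or a higher one. It is a problem for a subject below it, and the only level below 100 mg is 50 mg, which is reached through a safety-driven reduction. The instruction therefore raises the dose in exactly the subjects for whom a lower dose had been judged necessary. Its trigger, a falling white-cell count, meets none of the conditions that the protocol elsewhere sets for going back up.

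What is at stake is individual safety: renewed toxicity, or a higher dose in someone with a serious or repeated QT event. There is also a compliance problem. Section 7.2 defines an oral overdose as any excess over the dose the protocol specifies for the subject. Where two sections specify different doses, a site cannot tell whether 100 mg is correct or a reportable overdose.

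**Working it through.** The plan states no figure to reproduce on this point. The check compares the rules and takes one ratio.

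**Inputs**

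- Resumption dose after leukocytosis: 100 mg daily (Section 7.2.1.3).
- Dose levels in use: 50, 100, 150 and 200 mg daily (Section 7.2.1.2).
- Planned AG-221 arm: 158 subjects (Section 9.3).

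**Step 1: ratio of resumption dose to dose before interruption**

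| Dose before (mg) | Resumed as written (mg) | Ratio | Resumed at min(100, prior dose) (mg) | Ratio |
|---|---|---|---|---|
| 50 | 100 | 100/50 = 2.00 | 50 | 1.00 |
| 100 | 100 | 100/100 = 1.00 | 100 | 1.00 |
| 150 | 100 | 100/150 = 0.67 | 100 | 0.67 |
| 200 | 100 | 100/200 = 0.50 | 100 | 0.50 |

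As written, the dose rises at 1 of 4 levels. With a cap at the prior dose it rises at 0 of 4, and only the 50 mg row changes.

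**Step 2: who is on 50 mg, and may that subject go back to 100 mg?**

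| How 50 mg was reached | Existing rule on returning to 100 mg | Does WBC below 30 × 10⁹/L satisfy it? |
|---|---|---|
| Toxicity reduction, never escalated | To augment response, if 100 mg is tolerable | No |
| Reduced after earlier escalation | Only with morphologic relapse or PD | No |
| Grade 3 QTcF, no electrolyte or drug cause | Not allowed | No; direct contradiction |
| Second QT prolongation | Not allowed | No; direct contradiction |
| First Grade 2 QTcF event | Allowed after at least 14 days at Grade 1 or lower | Outside this point |

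In the two contradiction rows, a site that resumes treatment must break one rule: 100 mg breaks the QT rule, 50 mg breaks the leukocytosis rule. Nothing in the protocol says which prevails.

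**Step 3: possible reach**

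The documents give no counts. As assumptions only, take 5% to 20% of the arm on 50 mg, and 2% to 10% of those interrupted for leukocytosis:

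- low: 158 × 0.05 × 0.02 = 0.16 subjects
- high: 158 × 0.20 × 0.10 = 3.16 subjects

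The direct QT contradiction should be rarer still. Exclusion criterion 19 removes subjects with a screening QTcF of 450 ms or more, and Section 8.2 prohibits listed QT-prolonging drugs during AG-221 treatment.

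**The case against.** The strongest reply is that this is a drafting gap and not a wrong rule. The toxicities in Section 7.2.1.3 feed the dose rules of Section 7.2.1.2, where the default after a related toxicity is to resume one level lower. Against that default, naming 100 mg makes sense: a subject on the starting dose need not be reduced for leukocytosis, and one on 150 or 200 mg steps down. That is a plausible intent, but the text does not limit itself to those subjects.

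Four further points deserve weight.

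- **Discontinuation.** A subject who cannot tolerate 50 mg is to stop treatment. If uncontrolled leukocytosis at 50 mg is judged intolerance, the doubling never arises. That is a judgement and covers only some cases.
- **Medical Monitor.** Section 7.2.1.2 tells the investigator to seek guidance on dose changes if needed. An explicit milligram instruction gives a site little prompt to ask, and contact is not required at this step.
- **Returning to 100 mg is sometimes permitted.** This is true, but always on conditions that the leukocytosis rule omits.
- **Rarity.** The direct QT conflict needs a qualifying QT event, a reduction to 50 mg specifically, and then leukocytosis that hydroxyurea does not improve, interruption and recovery. A QT reduction to 150 or 100 mg creates no conflict. A careful site might also read the express QT prohibition as overriding.

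The amendment summary says the Section 7.2.1.3 toxicity updates follow the Investigator's Brochure. That document was not available, so whether it covers subjects on a reduced dose could not be checked. These points limit how often harm could follow. They do not change what the sentence directs.

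**Conclusion.** The concern holds. The leukocytosis rule gives the wrong dose for a subject on 50 mg: +100%, without any of the conditions that the protocol attaches to re-escalation elsewhere. It contradicts the QT rules outright after a second QT prolongation, or after a Grade 3 event without the stated exception. The doubling is what the text directs; whether sites would carry it out is not known. The estimated reach rests entirely on the assumed rates. Sample size, power, Type I error and the planned efficacy analyses are untouched. This should be corrected as a dosing-safety inconsistency, but it is not a threat to the trial's conclusions.

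**What to change.** Replace the resumption instruction in the Noninfectious Leukocytosis rule with:

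> *resume enasidenib at 100 mg daily or at the dose taken before the interruption, whichever is lower, when WBC is less than 30 × 10⁹/L; any later increase must meet the conditions in Section 7.2.1.2 and the QT Prolongation rules.*

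This keeps the step-down from 150 and 200 mg and removes the only dose increase. The cost is one sentence, by clarification letter or in the next amendment, with no change to data collection or to the planned analyses.
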